In the present study, we aim to compare the diagnostic yield of Robotic-nCLE-guided TBNA for lung cancer diagnosis to conventional Robotic-guided TBNA using the final diagnosis (histology or follow-up) as the standard reference. Furthermore, we will create an image atlas of the characteristics of nCLE-images in PPNs. Also, we aim to describe tumor types based on in-vivo characteristics. Improved characterization of distal lung lesions might lead to improved and quicker cancer diagnosis and patient care.

Background: nCLE imaging of PPNs under bronchoscopic guidance is feasible and safe.

Primary objective:

To compare the first-pass diagnostic yield of the sequential needle passes (ROSE) between the Robotic-nCLE-guided TBNA arm and the Robotic- guided TBNA arm in PPNs.

Primary endpoint:

Increase of the first-pass diagnostic yield by 20%, from 70% to 90%, between Robotic-nCLE-guided TBNA arm and the Robotic- guided TBNA arm in PPNs.

Secondary objectives:

1. To compare the per-patient diagnostic yield (cumulative pass diagnostic yield: cumulative number of passes until five cumulated passes) of Robotic-nCLE-guided TBNA arm to that of Robotic-guided TBNA arm in PPNs.
2. To compare the proportion of patients with lung cancer treatment in the Robotic-nCLE-guided TBNA arm to that of the Robotic-guided TBNA arm in PPNs.
3. To compare the proportion of patients with follow-up (video-assisted thoracoscopic surgery (VATS) or TTNA or TBNA procedures) in the Robotic-nCLE-guided TBNA arm to that of the Robotic-guided TBNA arm in PPNs.
4. To compare the number of passes needed to obtain a final diagnosis of Robotic-nCLE-guided TBNA to that of Robotic-guided TBNA in PPNs.
5. To assess the diagnostic performance (sensitivity, specificity, PPV, NPV, accuracy) of the sequential cumulative nCLE passes and the sequential cumulative ROSE passes using the final diagnosis as a reference.
6. Feasibility: obtain adequate CLE video footage in >80% of the PPN punctures.
7. To assess the safety of nCLE imaging, as defined by:
 - a. The number and frequency of all AE/SAE from the start of the procedure until end of 12-month follow-up;
 - b. The number and frequency of nCLE procedure-related AE/SAE from the start of the procedure until end of 12-month follow-up.
8. To assess the reproducibility of nCLE criteria with regard to the reference standard. Three nCLE characteristics for the detection of malignancy were identified during Wijmans et al. study [10]:

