The biopsy results can be classified into three categories: positive results, including malignant or benign lesions confirmed by a follow-up period, or negative results, including [18] intermediate histological samples, such as chronic inflammation, organizing pneumonia, or atypical cells without sufficient features to ascertain malignancy; or [22] indeterminate samples, such as normal lung tissue or insufficient sample size [6]. The tissue samples that produce intermediate and indeterminate samples should be further evaluated according to recommended guidelines for the management of pulmonary nodules.

In this study, the diagnostic yield of the bronchoscopic procedure (Robotic-guided TBNA or Robotic-nCLE-guided TBNA) will be defined as the proportion of patients in whom the bronchoscopic procedure yield a definitive diagnosis out of the total number of patients that have received the diagnostic procedure. This value is affected by the lesions' sizes, locations, and the existence of a bronchus sign or an airway leading directly into the lesion [23].

Primary objective:

To compare the first-pass diagnostic yield of the sequential needle passes (ROSE) between the Robotic-nCLE-guided TBNA arm and the Robotic-guided arm in PPNs.

Secondary objectives:

[figure not shown]
1. To compare the per-patient diagnostic yield (cumulative pass diagnostic yield: cumulative number of passes until five cumulated passes) of Robotic-nCLE-guided TBNA to that of Robotic-guided TBNA in PPNs.
2. To compare the proportion of patients with lung cancer treatment in the Robotic-nCLE-guided TBNA arm to that of the Robotic-guided TBNA arm in PPNs.
3. To compare the proportion of patients with follow-up (video-assisted thoracoscopic surgery (VATS) or TTNA or TBNA procedures in the Robotic-nCLE-guided TBNA arm to that of the Robotic-guided TBNA arm in PPNs.
4. To compare the number of passes needed to obtain a final diagnosis of Robotic-nCLE-guided TBNA to that of Robotic-guided TBNA in PPNs.
5. To assess the diagnostic performance (sensitivity, specificity, PPV, NPV, accuracy) of the sequential cumulative nCLE passes and the sequential cumulative ROSE passes using the final diagnosis as a reference.
6. To assess the feasibility by obtaining adequate CLE video footage in >80% of the PPN punctures.
7. To assess the safety of nCLE imaging, as defined by:

- a. The number and frequency of all AE/SAE from the start of the procedure until end of 12-month follow-up

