nCLE requires the administration of exogenous fluorescent contrast. Minutes before CLE positioning, the patient will be administered 2.5 mL of 10% fluorescein IV. A repeat dosage of 2.5 ml of 10% fluorescein can be provided after 15-30 minutes to a maximum dosage of 5 ml of 10% fluorescein in total. Patients will be monitored for allergic reactions, including anaphylaxis. Fluorescein Sodium can be used as a contrast agent with Cellvizio® I.V.E system with Confocal Miniprobes™ without change of formulation, mode of action, approved dose, or route of administration. Refer to the indications for using the fluorescein to perform the injection or to chapter 1: "Fluorescein Angiography: Basic Principles and Interpretation" of Ryan et al. book on Optical Imaging Technologies [25].

The target area will then be identified on the ultrasound and/or fluoroscopy monitor and accessed in the usual manner per standard of care. Once the nodule is localized, an 18G needle with the Confocal Miniprobe™ inside will be introduced through the bronchoscope's working channel and advanced into a lung nodule. After the puncture, the AQ-Flex™ 19 N Confocal Miniprobe™ will then be advanced through the needle into the nodule. Imaging will take place, which will be evaluated by the physician performing the procedure. The on-site image interpretation will be recorded. The AQ-Flex™ 19 N Confocal Miniprobe™ will be removed, and tissue will be aspirated at the imaging site from the tip of the needle that is still in place. ROSE will be performed by the cytology team per standard of care. If no lesional tissue is identified, then the robot may be repositioned for additional needle passes. For each needle pass, a separate CLE movie will be recorded. Multiple needle passes and nCLE imaging may occur, specifically if no tumor is identified on ROSE. In the case of re-localization of the needle, nCLE imaging may be repeated before further needle aspirations. Duration will be recorded after each pass. Chest ultrasound or fluoroscopy will be performed to evaluate for pneumothorax.

7. Puncture the identified target lesion with the needle per standard of care and usual procedure (the Confocal Miniprobe™ is pre-loaded but retracted)	8. Maintain the needle as straight as possible and parallel to the working channel of the scope. (to limit the retraction of the probe within the working channel) Twist the locking device and the probe back onto the needle
	

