Microscopic, real-time image sequences are recorded, and cellular structures are visualized as desired. If at any time the ~3 mm Confocal Miniprobe™ protrusion interferes with the TBNA procedure, the Confocal Miniprobe™ can be pulled back into the needle by unlocking the purple screw to change directions, and then advanced again and locked. As long as the white screw remains locked, the Confocal Miniprobe™ cannot be advanced further than ~ 3mm beyond the distal needle tip and will not be damaged.

Retrieval of the probe

When the physician has completed imaging tissue with the Confocal Miniprobe™, it can be removed from the needle by unlocking the purple screw and extracting the probe. The locking device is a single-use device and is discarded after the procedure.

9. After imaging, extract the Confocal Miniprobe™ and locking device assembly from the needle	10. Remove the locking device from the Confocal Miniprobe™ and discard it
-----------------------------------------------------------------------------------------------	---------------------------------------------------------------------------

Further biopsies may then be performed with a 20 g needle, forceps, or brush per standard of care at the discretion of the bronchoscopist. After the biopsies, a bronchial-alveolar lavage may be performed per standard of care at the discretion of the bronchoscopist. Endobronchial ultrasound (EBUS) with lymph node biopsies will also be performed when indicated as part of the standard of care.

If a second lesion requires a biopsy, the bronchoscope will be withdrawn, and the chest will be imaged by fluoroscopy or chest ultrasound to rule out pneumothorax per standard of care. The bronchoscope can then be re-inserted, followed by navigation to the second lesion. However, only one lesion will be imaged with nCLE per patient.

After the Cellvizio® procedure

After removal of the Confocal Miniprobe™, the tissue can be routinely aspirated per the standard TBNA procedure and analyzed for chemistry, cytology, and/or tumor markers. nCLE imaging will not interfere with tissue / fluid specimen collection during the remainder of the conventional TBNA procedure.

Steps of standard - and study (in bold) procedures:

1. Patients will be sedated following standard procedure.
2. **(research-purposes) After starting the procedure, we will administer 2.5 ml of fluorescein 10% intravenously to visualize the CLE images only in the patients in the Robotic-nCLE-guided TBNA arm).**

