- Twelve months follow-up data: repeat diagnostic procedures or new diagnoses on any lung nodule evaluated during the initial bronchoscopic index procedure, as well as healthcare utilization since the bronchoscopic index procedure (including healthcare visits, repeat bronchoscopic procedures, transthoracic biopsy, bronchoscopy, chemotherapy, brachytherapy, radiation therapy, surgical resection, and lymph node dissection).

nCLE image quality:

nCLE image quality for each nodule will be rated by the interventional pulmonologist as:

- **Very poor:** impossibility to observe any structure or criteria
- **Poor:** The observed criteria and structures are hardly recognisable and interpretable
- **Moderate:** Structures and criteria are recognisable and interpretable with close attention, but confidence in the interpretation remains low (may require replaying the sequence frame by frame)
- **Good:** Image quality is sufficient to enable an easy structures and criteria observation and interpretation (may require replaying the sequence frame by frame)
- **Very good:** criteria and structures are recognisable and interpretable very easily

Diagnostic and Therapeutic Management

Lung cancer treatment options are the following:

- **Minimally invasive surgery.** Thoracic surgeons can use minimally invasive techniques when possible, including [video-assisted thoracoscopic surgery \(VATS\)](#) and [robotic surgery](#). Surgeons remove the smallest amount of lung tissue necessary through wedge resection, sleeve lobectomy, and bilobectomy.
- **Highly targeted radiation therapy.** Radiation oncologists have access to the latest technology to carefully shape and precisely deliver radiation to the target. Targeted treatment is available through [intensity-modulated radiation therapy \(IMRT\)](#), volumetric modulated arc therapy (VMAT), [image-guided radiation therapy \(IGRT\)](#), and [proton therapy](#). These techniques reduce the risk of side effects and improve outcomes.
- **Carefully selected systemic therapy.** Mayo Clinic oncologists have access to various systemic treatments, including [chemotherapy](#), targeted therapy, and immunotherapy. Systemic treatments are selected using many factors, including the genetic makeup of your cancer cells.

[figure not shown]

Figure 3: Randomized controlled study device with two arms: Robotic-guided TBNA and Robotic-nCLE-guided TBNA with the different steps

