- Accuracy: Probability that a Robotic-guided biopsy gives correct prediction among the total number of cases examined: $= (a + d)/(a + b + c + d)$

Patient diagnostic and management analysis:

Intermediate and final diagnosis and management recommendation proportion differences for the two patient populations (Robotic-guided TBNA arm and Robotic-nCLE-guided TBNA arm) will be compared using a chi-square test. Intermediate and final diagnosis and management recommendation proportions will also be compared for the two patient populations. Differences between Robotic-guided TBNA and Robotic-nCLE-guided TBNA arms regarding the specific diagnostic and management categories will be compared using McNemar's test both at the intermediate diagnosis and the final diagnosis stage.

Feasibility statistical analysis:

The feasibility of needle-based lung cancer diagnosis will be assessed by investigating the following items:

- Assessing nCLE-image quality
- Assessing the feasibility of the integrated needle/Cellvizio® I.V.E Confocal Miniprobe™.

The imaging feasibility yield for the Robotic-nCLE-guided TBNA procedure is defined as the proportion of patients in whom procedure will yield at least good nCLE image quality out of the total number of patients that will receive that procedure.

The mechanical feasibility yield for the Robotic-nCLE-guided TBNA procedure is defined as the proportion of patients for whom Robotic-nCLE-guided TBNA procedure will be possible mechanically (meaning that the nCLE probe will be guided to the nodule successfully) out of the total number of patients that will receive that procedure.

Safety:

The safety will be assessed by carefully monitoring adverse events related to both procedures. Serious adverse event rates will be calculated by dividing the number of events for each procedure divided by the total number of procedures for each arm.

Reproducibility:

To assess the reproducibility of bronchoscopy guided nCLE:

- Estimating the reproducibility of nCLE criteria will be evaluated by calculating the inter-observer agreement of nCLE criteria between 3 readers (Fleiss Kappa).

In Wijmans et al. [10], three nCLE characteristics for the detection of malignancy were identified in different subtypes of lung tumors and metastatic lymph nodes:

- 1) dark enlarged pleomorphic cells;
- 2) dark cell clusters consisting of overlapping cell structures ('dark clumps'); and

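### The feasibility target is set per puncture, but Section 7 computes only a per-patient image-quality proportion, so the planned figure does not estimate the target

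*Combined protocol and SAP*

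**What the plan says.** **Target.** Secondary objective 6 in the Section 1 Summary is to "obtain adequate CLE video footage in >80% of the PPN punctures". The objectives list before Section 3 repeats it: "To assess the feasibility by obtaining adequate CLE video footage in >80% of the PPN punctures". It is the only secondary objective with a numeric criterion.

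**Analysis.** Section 7, Feasibility statistical analysis, defines the imaging feasibility yield as the "proportion of patients in whom procedure will yield at least good nCLE image quality". The denominator is everyone given the nCLE procedure. A mechanical feasibility yield follows, also per patient. Neither carries the 80% criterion, a test or a confidence interval.

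**Rating.** Section 6, nCLE image quality, states: "nCLE image quality for each nodule will be rated by the interventional pulmonologist as", followed by five levels from very poor to very good. None is called adequate, and the term is defined nowhere else. Section 5, Retrieval of the probe, adds: "However, only one lesion will be imaged with nCLE per patient". The operator's rating is therefore one per patient.

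**Passes.** Section 3 plans imaging at each sequential pass. Section 5, Steps during the procedure, states: "For each needle pass, a separate CLE movie will be recorded". The list of standard and study steps repeats imaging and sampling for each pass.

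**Second source of ratings.** Section 5, nCLE analysis, has three blinded raters review the videos, with image quality among the items.

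**The concern.** The objective and its analysis differ in three respects: the unit (puncture or patient), the quality standard ('adequate' or 'at least good') and the threshold (above 80% or none). Because several passes per patient are possible, the first difference changes the number reported. Section 7 does not say whether a patient with one good and two poor videos is a success.

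At stake is the feasibility claim. With the unit, the quality cut and the aggregation rule all open, the same videos could be reported as meeting or missing the target, and the choice could be made after the data are seen. The primary comparison is not affected.

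**Working it through.** **Inputs from the documents**
- Target: more than 80% of punctures (objective 6).
- nCLE arm: 59 patients (Section 4, Sample size calculation).
- First-pass yield: 70% in the control arm and 90% in the nCLE arm (same place).
- Sampling ends when ROSE finds sufficient material or the physician judges the passes enough (Section 3).
- Yield is tabulated up to five passes (Section 4). This is not stated as a cap on sampling.

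The documents do not forecast the number of passes per patient, so the results below are conditional on it.

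**The plan's own figure.** The unpooled normal approximation gives (1.960 + 0.842)² × (0.7×0.3 + 0.9×0.1) / 0.2² = 58.87, rounded up to 59 per arm, as stated. The number was set for the primary endpoint. Feasibility has no sample size calculation of its own.

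**Every patient has k passes, independent, each good with probability p**
- Any-pass rule: the patient proportion is 1 − (1 − p)^k. Setting this to 0.80 gives p = 1 − 0.2^(1/k).
- All-pass rule: the patient proportion is p^k.

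| k | p giving 80% of patients, any-pass | Patients if p = 80%, all-pass |
|---|---|---|
| 1 | 80% | 80% |
| 2 | 55% | 64% |
| 3 | 42% | 51% |
| 5 | 28% | 33% |

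The two rules err in opposite directions.

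**Passes end by ROSE.** Assume that each pass ends sampling with probability y, equal to the first-pass yield and independent of image quality. With q = 1 − p:
- Any-pass rule: the patient proportion is 1 − yq/(1 − (1 − y)q). Setting it to 0.80 gives q = 0.2/(y + 0.2(1 − y)).
  - y = 0.9: q = 0.2/0.92 = 0.217, so p = 78%.
  - y = 0.7: q = 0.2/0.76 = 0.263, so p = 74%.
- All-pass rule at p = 0.8: the patient proportion is yp/(1 − (1 − y)p).
  - y = 0.9: 0.72/0.92 = 78% of patients.
  - y = 0.7: 0.56/0.76 = 74% of patients.

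Mean passes are 1.11 and 1.43. Under this assumption the gap is 2 to 6 points in either direction.

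**A mixed case, for illustration.** If half the patients have one pass and half have three, the any-pass rule gives 80% of patients when 0.5q + 0.5q³ = 0.2. Then q = 0.355 and p is about 64.5%.

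**Counting bound under the any-pass rule.** At least 48 of 59 patients (81.4%) are needed to exceed 80%, so there are at least 48 good punctures. Suppose no patient has more than five passes.
- 90% stop after one pass: at most 53 + 6×5 = 83 punctures, and 48/83 = 58% good at the least.
- 70% stop after one pass: at most 41 + 18×5 = 131 punctures, and 48/131 = 37% good at the least.

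**Quality standard.** Section 6 describes 'Moderate' images as still interpretable, though with low confidence. They fail 'at least good'. If 'adequate' includes them, Section 7 is the stricter standard, whatever the unit.

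**The case against.** **The lenient direction is not in the text.** A reader might infer that one good pass makes a patient a success, so that the target can be met while most punctures fail. Section 7 contains no such rule. The single rating per nodule could equally be an overall score, or every pass might have to be good, and excluding 'Moderate' images also works against leniency. This objection stands.

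**Large distortions need many passes.** A 60% puncture rate becomes 84% or 94% of patients only if everyone has 2 or 3 independent passes (1 − 0.4², 1 − 0.4³). With ROSE-based stopping it becomes 1 − 0.36/0.96 = 62.5% at 90% yield, or 1 − 0.28/0.88 = 68% at 70%. Positive correlation between passes in one nodule would narrow the gap further. This too stands, with a limit: Section 5 expects further passes when ROSE shows no tumor, and Section 4 assumes a malignancy prevalence of 0.5. More passes than the yield suggests are therefore plausible.

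**The patient figure is not said to be judged against 80%.** Correct, but then nothing in Section 7 is, and objective 6 has no analysis.

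**'Punctures' might mean punctured nodules, one per patient.** The step list inserts the needle once and repeats only imaging and sampling. This reading is strained, because Steps during the procedure has the robot repositioned for additional needle passes. Even if accepted, it leaves 'adequate' undefined and the 80% criterion unused.

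**The impact is limited.** Feasibility is a single-arm secondary objective and is not among the Section 8 endpoints. Per-pass quality may already be recoverable from the blinded review. Both points lower the stakes, but they do not make the analysis match the objective.

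**Conclusion.** The mismatch is in the text and needs no assumption: followed as written, Section 7 does not estimate the proportion of punctures with adequate footage and does not compare it with 80%.

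The size and direction of the error are undetermined. They depend on the aggregation rule, the meaning of 'adequate' and the number of passes, none of which the documents fix. Under independence, 80% of patients can stand for 55% or 42% of punctures (any-pass rule, 2 or 3 passes for everyone), while a true 80% can appear as 51% of patients (all-pass rule, 3 passes). If stopping follows the planning yields independently of image quality, the gap is only a few points.

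The documents do not support a claim that the plan is lenient or would pass when most punctures fail. Under the any-pass rule with 90% stopping after one pass and at most five passes, that outcome is out of reach. It becomes possible at 70%. The point should be corrected, but it concerns a secondary objective only.

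**What to change.** Make the Section 7 imaging feasibility yield match objective 6:

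1. Define 'adequate' as one fixed cut on the five-level scale in Section 6, before any video is scored for this purpose.
2. Use a quality rating for every recorded pass video, and state whose rating counts. The blinded raters already review videos for image quality.
3. Take all attempted nCLE punctures as the denominator, and count failed or missing video as inadequate.
4. Report the proportion against 80% with a 95% confidence interval that allows for clustering of punctures within patient.
5. Keep the per-patient yield as a separate descriptive figure, with its aggregation rule written down.

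The cost is revised wording and slightly more analysis work. No extra patient procedure is needed, and the sample size and primary endpoint do not change. The feasibility figure may turn out less favourable.
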